4.7.2 SDM processes

To assess SDM processes the recordings of the clinical encounter will be evaluated (video/audio or audio only recordings).

Extent of SDM that took place during the encounter will be assessing the degree of involvement of patients by the clinician in SDM using the OPTIONS scale.⁵³ The scale consists of 12 items scored from 0, no effort to 4, exemplary effort. The 12 items are summed and converted to a 100 point scale. A sample of 20% of the recordings will be assessed by two or more reviewers. Agreement will be assessed by Lin's concordance index⁵⁴, where any value over 0.8 will be considered concordant. If concordance does not occur within the first 20%, the two reviewers will assess cases of difference and review an additional 10 cases to test for agreement. Recordings scored by both reviewers will be averaged.

Impact of SDM on Encounter will be assessed by comparing the length in minutes of the discussion about anticoagulation and of the office visit, when available. Study coordinators when possible will time the encounters in intervention and control visits, prioritizing those encounters in which recording was not allowed. Potential issues preventing assessment of time may be recruitment of another patient.

Fidelity of SDM Tool by the clinician will be assessed by a review of the recording looking for key items to be addressed. A checklist of key elements will be assessed in both arms to assess not only the fidelity but potential contamination. A sum of the components in the checklist will be calculated for each recording and compared between arms. To score the recording first a sample of 20% of the video's will be assessed by two reviewers. Agreement will be assessed by Lin's concordance index⁵⁴, where any value over 0.8 will be considered concordant. If concordance does not occur within the first 20%, the two reviewers will assess cases of difference and review an additional 10 cases to test for agreement. Recordings scored by both reviewers will be averaged. For encounters where

audio and video recording has been declined, a real-time assessment will occur at the consent of the clinician and the patient. The study coordinator will conduct these real-time reviews.

Inclusion of Cost as an Element of SDM Process will be assessed by first using qualitative inductive content analysis of the transcripts of video-recorded clinical encounters to describe the scope of cost conversations. Deductive video-graphic analyses will be used to code the occurrence of cost conversation themes in order to determine the impact that Anticoagulation Choice has on the appearance of these themes, controlling for individual characteristics and contexts, and the association between cost conversation themes and SDM quality (described above), SDM Processes (described above), and Anticoagulation Use (described below).

4.7.3 Anticoagulation Use

Rate of anticoagulation: The key indicator of the choice to start an anticoagulant will be its prescription in the EMR prescription module (observed discussions and patient/clinician accounts may not reflect decisions confirmed after the visit with a prescription, for example, after the clinician or the patient checked other information or with other informants). After this primary ‘decided as prescribed’ approach, we will conduct secondary analyses using patient/clinician reported and video-observed decisions. Decisions may be for starting or not an anticoagulant in the start cohort. It is possible that there may be some decisions to stop anticoagulation in the review cohort, but we expect start and review cohorts to contribute information about choice of anticoagulant.

Choice of anticoagulant: We will review the EMR and 10-month pharmacy profiles (to stand for the 12-month profile given the automatic expiration of pharmacy records at 1 year) to determine the prescribed anticoagulant and whether and when switches to another agent or to no anticoagulant took place.

Together, they should capture choice and switches even when these occur as a result of changes in clinician (e.g., from cardiology to primary care). When available, we will note the documented reasons from clinical notes for choosing and switching as well as with which clinician the change was made (e.g primary, cardiology, etc.).

Anticoagulation persistence: Patients will identify the pharmacy(-ies) they use to fill their prescriptions and authorize us to obtain their prescription drug fill data. We will calculate anticoagulation persistence, using the percent days covered (PDC) based on prescription refill behaviors (total days supply of anticoagulant filled / total days of observation from the first prescription fill date; range 0-100%). We will also pull all pharmacy refills for the 12 months prior to enrollment. This will allow us to calculate persistence for prior use of anticoagulants for the review cohort to compare to persistence post encounter and see if there is an impact.

Warfarin use: For patients who choose to stay on warfarin, we will also use as secondary measures of adherence: (a) the proportion of INR tests obtained/scheduled; and (b) percentage of time at therapeutic target (typically INR 2-3).

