Data to be collected on patients include variables necessary to estimate the risk of stroke and bleeding, age, gender, BMI, smoking status, alcohol consumption, marital status, annual income of household, highest level of education, residency (nursing home), location of primary healthcare and total number of medications patients is currently taking. To further characterize the patients, we will use Chew et al single-item health literacy screener,⁴⁶ a 4-item modified Subjective Numeracy Scale,^{47, 48} and a single-item health status measure.⁴⁹

We will collect information on past use of anticoagulants through medical record review. We will categorize the patients into two cohorts for descriptive and analytical purposes. For patients who are not using an anticoagulant at the time of trial participation will form the 'Start' cohort. They may have used anticoagulation and discontinued >6 months ago, never used anticoagulation, or are using aspirin only. Patients that began an anticoagulant

within the past 10 days of the enrolled encounter that were prescribed an anticoagulant within the emergency department or an inpatient visit will still be considered a new ‘Start’.

Patients who are on warfarin or NOACs or used them in the past 6 months will form the ‘Review’ cohort. This cohort may include patients who have difficulty maintaining a therapeutic INR, or patients considering switching to a different anticoagulant or to stay on warfarin but switch to home INR monitoring.

The post consent survey for clinicians will collect demographic data (age, gender, specialty, % of their practice dedicated to anticoagulation care).

Calendar of Events

	Prior to Study Enrollment	Prior to Encounter		Post Encounter	12 months Post Enrollment
Patient Completed Forms			R A N D O M I Z E D A T I O N		
Informed Consent	X				
Pharmacy Consent	X				
Survey				X	
Phone ¹					X
Clinician Completed Forms					
Informed Consent	X				
Survey		X		X	
Clinical Data Abstracted from EMR					
Bleeds					X
Strokes					X
INR Tests (# and values outside of 2-3 range)					X
Anticoagulation Prescription		X		X	X
Pharmacist Request					
Anticoagulation					X ²

Use					
-----	--	--	--	--	--

- 1- Patients who do not have utilization within enrolling healthcare system will be contacted via phone for verification of safety data (strokes and bleeds). If no information in the record and follow-up is necessary we will call patients the maximum number allowed by the IRB followed by a postal survey

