- 2- Pharmacist records will be requested for 12 months prior to enrollment through 10 months post enrollment.

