4.8 Follow-up Guidelines

All patients will be followed per protocol guidelines and deviations from protocol will be reported to the IRB.

Withdraw: If a patient refuses to continue to participate and they withdraw consent they will then be considered withdrawn from the study; to uphold the intention-to-treat principle, we will inquire as to whether we can continue to passively collect data from the medical record, and if ok from 10-12 month pharmacy profiles and patient surveys. If not, then no further data will be collected through medical review or self-report. Data collected prior to withdraw will be utilized unless expressly told otherwise by the patient.

Ineligible: If a patient enrolled onto the study has been found ineligible (not meeting one of the eligibility criteria) they will be documented for reason of ineligible in the study chart. These patients will continue to receive the intervention and all data will be collected for the study. This is a safe course of action as the intervention does not pose any potential harm to the patient beyond loss of privacy. The patients will be identified in the results as being ineligible and reason but will be included in all analyses.

The procedure for post-randomization exclusions will involve presenting the case to the trial PI blind to the participant's allocation and to their results.

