We expect approximately 90% of patients to start (start cohort) or continue a medication (review cohort). Of those, we can reasonably expect to obtain >85% of the pharmaceutical records for those (records will be requested of all enrolled patients regardless of decision). Thus, using the trial size estimated of **999 participants**, we will have ~765 patient records available for assessment of anticoagulant persistence at 12 months (PDC). In our review of the Optum database, 40% of patients were adherent to anticoagulation (>80% PDC, the threshold used by CMS) at 12 months. Assuming an expected rate of 60% PDC for the usual care cohort, we would have 80% power to detect a 9% difference (69% PDC in the SDM tool arm), with a two-sided test and an alpha of 0.05. In subgroup analyses comprising 100 participants per arm and using a one-sided test and alpha of 0.05, we will have 80% power to detect differences of at least 16%.

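### A stated 1-year expiry of pharmacy records does not fit a 22-month fill window with one request at follow-up; the plan should date the pre-enrolment request and say what expires

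*Combined protocol and SAP*

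**What the plan says.** All references are to the combined protocol and SAP.

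- **Length of the follow-up profile.** Section 4.7.3, under choice of anticoagulant: "We will review the EMR and 10-month pharmacy profiles". The 10 months are openly a substitute for 12, "given the automatic expiration of pharmacy records at 1 year".
- **Pre-enrolment fills.** Section 4.7.3, under persistence: "We will also pull all pharmacy refills for the 12 months prior to enrollment". No date is given for this pull. Its purpose is stated: "This will allow us to calculate persistence for prior use of anticoagulants for the review cohort to compare to persistence post encounter".
- **Request window.** Section 4.6, footnote 2 to the Calendar of Events: "Pharmacist records will be requested for 12 months prior to enrollment through 10 months post enrollment".
- **Request timing.** In the calendar, the block headed "Pharmacist Request" carries one mark, tied to footnote 2, in the column for 12 months after enrolment. There is no mark at or before the encounter. Section 4.8, on withdrawal, speaks of "10-12 month pharmacy profiles".
- **Authorisation.** Section 4.2.3 has patients authorise release of pharmacy records during consent, and the calendar places pharmacy consent before enrolment.
- **Naming of the outcome.** Aim 2 and section 4.9.2 both describe persistence at 12 months.

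**The concern.** The same limit is used in one place and ignored in another. If a record cannot be obtained once it is a year old, that may be a reason to shorten follow-up to 10 months. It is then also a reason why a request sent at follow-up cannot reach back to the year before enrolment. If records do last long enough to return 22 months, the reason given for the shorter profile fails. Either way the text needs reconciling.

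What is at stake is one analysis: percent days covered (PDC) before the encounter against PDC after it in the review cohort. With two pre-enrolment months or fewer, the prior PDC would rest on one or two fills if fills are roughly monthly (an assumption; the plan gives no fill length), set against 10 months afterwards. The review cohort also includes patients whose last use was up to 6 months before enrolment. Those who stopped 3 to 6 months before could show no prior fills at all in so short a window. Under that reading of expiry the loss cannot be repaired later, so the timing of the request matters more than it would for a chart abstraction.

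**Working it through.** **Inputs**

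- Pre-enrolment fills wanted: 12 months (section 4.7.3; section 4.6, footnote 2).
- Post-enrolment fills wanted: 10 months (same places).
- Retention R: 12 months, reading section 4.7.3 as a rolling one-year look-back. This is an assumption, because the plan does not define expiry.
- Month of request t: 10 to 12, from the single calendar mark and the wording of section 4.8. This too is inferred.

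**Step 1: the span.** 12 + 10 = 22 months. The plan does not print this total, but it follows from footnote 2. With R = 12, no single request can return more than 12 of the 22 months.

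**Step 2: what a request at month t returns.**

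- Pre-enrolment months = max(0, min(12, R − t))
- Post-enrolment months = min(t, 10) − max(0, t − R)

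With R = 12:

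| Request at month | Pre-enrolment months | Pre-enrolment share lost | Post-enrolment months |
|---|---|---|---|
| 0 | 12 − 0 = 12 | 0% | 0 |
| 10 | 12 − 10 = 2 | 10/12 = 83% | 10 |
| 12 | 12 − 12 = 0 | 12/12 = 100% | 10 |

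A request at month 0 plus one at month 10 covers all 22 months.

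**Step 3: dependence on retention.** The longer values of R are assumed, to show how the result moves. Entries are pre-enrolment months returned out of 12.

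| R (months) | Request at month 10 | Request at month 12 |
|---|---|---|
| 12 (stated) | 2 | 0 |
| 18 | 8 | 6 |
| 22 | 12 | 10 |
| 24 | 12 | 12 |

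A single follow-up request recovers the whole pre-enrolment year only if records last at least 22 months (request at month 10) or 24 months (request at month 12).

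**Step 4: what is untouched.** All 10 post-enrolment months come back in both follow-up rows of the first table. The plan's count of records for the persistence analysis, 999 × 0.90 × 0.85 = 764.2 against the stated figure of about 765, does not depend on pre-enrolment fills.

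**The case against.** The strongest reply is that expiry is never defined. The plan does not say what expires or from when the year runs. If what lapses is access under the authorisation signed at consent, a request at month 10 falls inside the year with a margin, and fills from month −12 to month +10 could all be obtained. That reading makes the 10-month profile and footnote 2 agree. It also has one advantage over the look-back reading: with a rolling 12-month look-back, a request at month 12 would return all 12 post-enrolment months, so the shorter profile would serve only as slack for late requests. Against it, the text says that records expire, not permission, so this reading is an inference as well.

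The second reply is about timing. The sentence on pre-enrolment refills carries no date, footnote 2 gives a span and not a number of requests, and the calendar's 12-month column may be a nominal follow-up point. A pull at baseline that was never written down cannot be excluded and would remove the problem. No such pull is described anywhere, however.

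Both replies stand as limits. A reader might infer that most of the pre-enrolment fills will be lost. The documents do not support so flat a statement, because it needs the look-back reading and a single late request together. A reader might also infer that 12-month persistence is misreported. Section 4.7.3 discloses the 10-month substitute under choice of anticoagulant, so what remains is that Aim 2 and section 4.9.2 do not repeat it. Neither reply removes the need to reconcile the text.

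**Conclusion.** The inconsistency stands: a one-year limit on pharmacy records, a 22-month window and one request marked at follow-up do not fit together as written. If records older than a year are unavailable and the only request goes out at month 10 to 12, just 2 to 0 of the 12 pre-enrolment months are returned (83% to 100% missing), and the review cohort's before/after PDC comparison could not be done as planned. If expiry refers to something else, the data may be safe and the reason given in section 4.7.3 is what needs correcting.

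The reach is narrow. The exposed analysis is a non-randomised secondary comparison within one cohort, with no power claim attached. It would be wrong to infer that the trial's main results, or its randomised persistence comparison, are compromised. The primary shared decision making outcomes use no pharmacy data, and the between-arm post-enrolment PDC keeps its 10 months even under the least favourable reading considered here. The point merits a change because the remedy is cheap and protects the comparison under either reading.

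**What to change.** 1. Request the 12 pre-enrolment months at enrolment, under the authorisation signed at consent, at least for the review cohort. Cohort is a stratification factor (section 4.9.3), so it is known at randomisation and the request can be targeted.
2. Request the post-enrolment months at about month 10.
3. Show both requests in the Calendar of Events and in footnote 2, and date the pre-enrolment pull in section 4.7.3.
4. State in section 4.7.3 what expires at one year and from when the year is counted.
5. As a minor wording point, carry the 10-month substitute through to Aim 2 and section 4.9.2.

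The cost is one extra records request for each pharmacy that a review-cohort patient names, and section 4.7.3 allows for more than one pharmacy per patient. If the start and review cohorts are of equal size, as section 4.9.2 assumes, that is about 999/2 ≈ 500 patients, fewer to the extent that patients decline the authorisation. The rest is wording. Patients have nothing further to do, since the study team contacts the pharmacies.

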1.0 Aims

The goal of this study is to determine the extent to which standard care plus the Anticoagulation Choice tool promotes shared decision making (SDM) and impacts anticoagulation uptake and adherence versus standard care without this tool in patients with nonvalvular atrial fibrillation (AF).

Aim 1. To what extent does use of the ANTICOAGULATION CHOICE tool promote high-quality SDM versus standard care?

Using encounter video recordings and post-visit patient and clinician questionnaires, we will assess **SDM quality** (primary endpoint) **and processes**.

We hypothesize that use of the tool will improve SDM irrespective of patient literacy/numeracy, stroke risk, anticoagulation use at baseline, or type of clinic.

Aim 2. To describe the impact Anticoagulation Choice tool has on the rate of anticoagulation, the choice of anticoagulant, and adherence to anticoagulation in at-risk patients with AF versus the impact of standard care.

Using medical records and pharmacy profiles, we will determine the choice of anticoagulation, changes in anticoagulant use over time, and 12-month drug persistence, in all patients and in subgroups defined by patient literacy/numeracy, stroke risk, anticoagulation use at baseline, and type of clinic. As safety outcomes, we will monitor serious bleeding or strokes requiring medical attention.

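### Persistence is called percent days covered but is defined as supply dispensed since first fill, so it can overstate coverage and gives never-fillers no value; its stated 80% power is about 74% if 60% and 69% are proportions adherent

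*Combined protocol and SAP*

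**What the plan says.** Section 4.7.3 (Anticoagulation Use) calls the persistence measure percent days covered (PDC) and defines it as "total days supply of anticoagulant filled / total days of observation from the first prescription fill date; range 0-100"%. It gives no rule for overlapping supply, supply left at the end of the window, or patients with no fill. The window is 10 months of pharmacy records standing in for 12, "given the automatic expiration of pharmacy records at 1 year". The same measure serves a before/after comparison: "This will allow us to calculate persistence for prior use of anticoagulants for the review cohort to compare to persistence post encounter".

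Aim 2 (section 1.0) includes "adherence to anticoagulation in at-risk patients with AF versus the impact of standard care". Section 4.9.1 promises an intention-to-treat analysis of everyone enrolled. Uptake is a separate outcome in section 4.7.3, measured by a prescription in the electronic record.

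Section 4.9.2 sizes the persistence comparison. It expects about 90% of 999 patients to start or continue a drug and adds "we can reasonably expect to obtain >85% of the pharmaceutical records for those", giving about 765 records, although records are requested for all enrolled patients. It cites a database in which "40% of patients were adherent to anticoagulation (>80% PDC, the threshold used by CMS) at 12 months". It then assumes 60% PDC under usual care and states "we would have 80% power to detect a 9% difference (69% PDC in the SDM tool arm"), two-sided at 0.05. For subgroups of 100 per arm, one-sided at 0.05, it states "we will have 80% power to detect differences of at least 16"%.

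**The concern.** There are two separate problems.

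**The definition.** A measure of days covered counts each calendar day once. The formula adds up supply instead, so it credits days outside the window and credits the same day twice when a second agent is dispensed before the first runs out. The error grows with fill length and with switching. Choice and switching of agent are themselves outcomes of this trial, so the overlap could differ by arm. The documents do not show whether it does.

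Starting the clock at first fill has a second effect. A patient who is prescribed but does not fill counts as treated under the uptake outcome and then drops out of persistence, so neither outcome records the failure to fill. A late first fill is not penalised. Filling happens after randomisation and may respond to the tool, so a comparison among those who fill is not protected by randomisation.

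**The power.** The sentence before the calculation speaks of a proportion of patients above 80% PDC. Read in the same way, 60% versus 69% does not give the stated power.

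**Working it through.** **A. The formula against days covered**

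The documents give no fill lengths and no frequencies, so these are illustrations under assumed fills. The window is W = 300 days (10 months) and each fill supplies L days.

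- Formula: total supply / W. Days covered: distinct days in the window with supply / W.
- Largest over-count from a last fill on day 299, with non-overlapping fills: (L − 1)/300 = 9.7, 19.7 and 29.7 points for L = 30, 60 and 90.
- Over-count from a switch of agent on day 10: (L − 10)/300 = 6.7, 16.7 and 26.7 points.

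| Fills | Formula | Days covered |
|---|---|---|
| 90-day, on days 0, 90, 180, 270 | 360/300 = 120% | 300/300 = 100% |
| 90-day, on days 0, 90, 270 | 270/300 = 90% | 210/300 = 70% |
| 90-day, agent A day 0, agent B days 10 and 100 | 270/300 = 90% | 190/300 = 63.3% |
| 30-day, eight consecutive, then day 299 | 270/300 = 90% | 241/300 = 80.3% |

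The last row is the worst case above 80% for non-overlapping 30-day fills. In a window of 304 or 305 days, with the last fill on the final day, it becomes 88.8% versus 79.3%, or 88.5% versus 79.0%. With such fills a patient can hardly land on the wrong side of an 80% line; with 90-day fills this is easy.

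Late start: a first fill on day 120 with full cover afterwards scores 180/180 = 100% from first fill and 180/300 = 60% from the encounter. With no fill there is no start date and so no value; the formula cannot return 0.

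**B. The stated power**

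Inputs from section 4.9.2: 999 × 0.90 × 0.85 = 764, which reproduces the plan's ~765; 60% versus 69%; two-sided 0.05. Equal arms (382.5 each) are assumed, and clustering by clinician is ignored.

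Pooled-variance test of two proportions, mean proportion 0.645:

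- SE under no difference: √(2 × 0.645 × 0.355/382.5) = 0.0346
- SE under the alternative: √((0.60 × 0.40 + 0.69 × 0.31)/382.5) = 0.0344
- Power: Φ((0.09 − 1.96 × 0.0346)/0.0344) = Φ(0.644) = **74.0%**, against 80% stated

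Other methods give much the same: unpooled 74.3%, arcsine 74.1%, exact power of the chi-square test 74.2%, continuity-corrected 71.5%.

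- 80% power needs about 885 records, or a difference of 9.7 points with 765.
- The 85% retrieval is a floor. Retrieval of 90% gives 809 records and 76.4%; 95% gives 854 and 78.6%; reaching 80% takes about 98.5%.
- Subgroup: 60% versus 76%, 100 per arm, one-sided 0.05, gives 78.6%, close to the stated 80%.
- If mean PDC was meant, power is Φ(9/(SD × √(2/382.5)) − 1.96): 87.5% at SD 40, 79.0% at SD 45, and 80% at SD 44.4. No SD is stated. The largest SD possible on a 0–100 scale is √(60 × 40) = 49.0 for a mean of 60 and √(69 × 31) = 46.2 for a mean of 69.

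**The case against.** *The name and the stated range show that ordinary PDC was intended, loosely worded.* That may be so, but the formula is what would be programmed. A cap at 100% leaves the 90% versus 70% and 90% versus 63.3% cases untouched.

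*The examples are extremes.* They are, and nothing in the documents says how often they occur. No 80% cut is specified for the trial's own analysis either. This limits what can be said about size; it does not repair the definition.

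*Persistence after first fill is a legitimate conditional measure, uptake is reported separately, and Aim 2 is worded as descriptive.* All true, and a reason to keep the measure. It still needs labelling as a comparison among fillers, and the prescribed-but-unfilled patient still appears in neither outcome. The imputation promised in section 4.9.1 is for missing values and does not settle an undefined one.

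*The power may refer to mean PDC.* The wording allows it. The subgroup figure does not decide the matter: with an SD of 44.4, mean PDC gives 80.0% for the main comparison and 81.7% for the subgroup. But that SD is close to the maximum possible for those means, and the preceding sentence is about a proportion. Proportions are the natural reading, and the 74% remains conditional on it.

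*999 is a minimum recruitment target.* It is, yet section 4.9.2 computes its power from 999. At 90% and 85%, 885 records would need about 885/0.765 = 1,157 enrolled, a number the plan does not promise.

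**Conclusion.** The concern holds on both parts and should be fixed; it does not touch the primary outcome.

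The definition is not percent days covered. It can exceed 100% and can overstate coverage below 100%, by up to 29.7 points for a late 90-day fill and 9.7 points for a late 30-day fill in a 300-day window. Early refills of the same agent matter only so far as the carried-forward stock runs past the window end. The measure leaves patients who never fill without a score, and the comparison it supports is not one of the groups as randomised. The size and direction of any bias in the trial result cannot be known from the documents.

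The stated 80% power is about 74% if 60% and 69% are proportions adherent, with equal arms and no clustering. If they are mean PDC, the figure cannot be checked without an SD.

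**What to change.** **Definition (section 4.7.3)**

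- Define PDC as calendar days covered, each counted once. Carry early-refill supply of the same agent forward, do not double-count overlap at a switch, and cut supply off at the window end.
- Divide by days observed, ending at month 10, death, or withdrawal of permission to use records.
- For the review cohort, start at the index encounter and count supply on hand where prior fills are retrieved. Where they are not, flag those patients and show results with and without them.
- Label PDC from first fill as a comparison among those who fill.
- Add a supplementary comparison from the index encounter in all randomised patients with authorised records. Score 0 only where records were retrieved and show no fill; unretrieved records stay missing and are not scored 0. Report an estimate with a confidence interval. State that it mixes uptake and persistence, so a 0 may reflect an informed decision not to take anticoagulation.

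**Power (section 4.9.2)**

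State the scale. If proportions, give about 74% power for 9 points, or 80% power for about 9.7 points. If means, give the SD.

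**Cost**

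Wording and programming, with no extra patients. Post-enrolment fills are already requested for everyone. Prior fills are also to be requested, but the Calendar of Events marks the pharmacist request only at 12 months while section 4.7.3 says pharmacy records expire at 1 year, so an earlier request may be needed.

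The supplementary comparison has lower power. Assume it is dichotomised, with 85% retrieval for everyone (999 × 0.85 = 849 records; the plan states 85% only for those who start or continue) and equal uptake in both arms. Then 90% uptake gives 54.0% versus 62.1%, about 67% power and a 95% interval of about ±6.6 points. Uptake of 80% gives about 56% power, and 95% gives about 73%.
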